8.2 Analysis of immune effector subset data

Immune effector subset expression, expression rate and activation state will be examined in tumor tissue, TDLNs and peripheral blood.

8.2.1 Tumor tissue

IHC analyses will be done on the pretreatment tumor biopsy and postinduction resection specimen of the primary tumor. The analyses include PD-1, PD-L1, CD4, CD8, FoxP3 and Ki67. Values will be quantified semi-quantitatively and compared within each patient (postinduction vs baseline) and between the treatment arms (SBRT vs SBRT + pembrolizumab) with the use of the Wilcoxon signed ranks test and the Wilcoxon-Mann Whitney test, respectively.

Immune cells will be isolated from the hilar and mediastinal lymph nodes in the resection specimen by the use of a cytologic scraping method as described in section 7.1.2.7.2. Values will be quantified on a linear scale and compared between the treatment arms (SBRT vs SBRT + pembrolizumab) with the use of the independent samples t-test.

The tumor surrounding non-tumor lobar lung tissue will be examined for radiation induced (fibrotic) changes. The percentage of fibrosis and immune cell infiltrate surrounding the tumor will be assessed semi-quantitatively and compared between the treatment arms (SBRT vs SBRT + pembrolizumab) with the use of the Wilcoxon-Mann Whitney test.

8.2.2 Immunophenotyping in peripheral blood

All parameters will be quantified on a linear scale and compared within each patient (baseline vs on-treatment vs post-induction vs post-surgery) and between the treatment arms (SBRT vs SBRT + pembrolizumab) with the use of the paired t-test and the independent samples t-test, respectively.

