5.2 Sample size

Twenty patients will be included in this study. A formal power analysis to calculate a sample size is not feasible due to the explorative nature of this trial. The sample size of 10 patients in each arm is based on two previous analyses that we performed. In a cohort of 9 head and neck cancer patients we were able to find significant differences in the expression of activation markers between different dendritic cell subsets (data on file). In a cohort of 9

melanoma patients we were able to find significant differences in the expression of activation markers between dendritic cell subsets of patients with a Breslow thickness more or less than 1.5 mm (60).

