6.0 TRIAL FLOW CHART

6.1 Study Flow Chart

Trial period	Screening Phase	Imaging	Induction treatment phase	Surgery	Follow-up
Scheduling Window (Days)	-30 to -1	-14 to 0	From day 1 to day 56 (2 weeks after 2 nd pembrolizumab cycle)	From day 56 to day 70	From surgery to 6 months thereafter
Administrative Procedures					
Informed Consent	X				
Eligibility Criteria	X				
Demographics and Medical History	X				
Prior and Concomitant Medication Review	X				
PET Imaging					
⁸⁹ Zr-pembrolizumab		X ^a			
Clinical Procedures/Assessments					
Review Adverse Events	X		X ^b		
Full Physical Examination	X				
Directed Physical Examination	X		X ^b		X ^c
Vital Signs and Weight	X		X ^b		
ECOG Performance Status	X		X ^b		
12-lead ECG	X				
¹⁸ F-FDG PET-CT		X		X	
Laboratory Procedures/Assessments					
Pregnancy Test	X				
Complete Blood Count (CBC)	X	X ⁱ	X ^b		
Comprehensive Serum Chemistry Panel	X		X ^b		
Urinalysis	X				
T3, FT4 and TSH	X		X ^d		
Treatment					
SBRT			X		
Pembrolizumab			X ^a		
Surgery				X	
Efficacy Measurements					
Tumor Imaging (CT thorax +/- abdomen and MRI brain)		X	X ^e		X ^f
Tumor Tissue and Blood analysis					
Core tumor biopsy	X				
EBUS FACS		X	X ^g		
Surgical resection specimen				X	
Immunophenotyping		X ^h	X ^h	X ^h	X ^h

X^a: only for patients randomized to the SBRT + pembrolizumab arm; X^b: every cycle; every 6 weeks; X^c: if indicated; X^d: after 2nd pembrolizumab cycle; X^e: within 2 weeks of surgery; X^f: following resection every 3 months for the first 2 years and every 6 months for the 3 years thereafter; X^g:; X^g:between week 2 and 3 after SBRT; . X^h: see section 7.1.2.10 for timepoints; Xⁱ: 72 and 144 hours post-injection for patients undergoing ¹⁸F-FGD-PET-CT

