7.1.2.10 Immunophenotyping on peripheral blood

To evaluate the pre- and on-treatment immune status, polychromatic flowcytometric analyses of lymphoid and myeloid subsets in peripheral blood will be performed at t = 0, 21 days (immediately prior to 2nd therapeutic dose), just before surgery, one week after surgery and after 6 months. Heparinized blood (40 ml) will be taken at each of these time points and PBMC isolated. The following 8-12 marker panels will be run on a BD LSRFortessa (with appropriate FMO controls): 1) Treg/effector T cell activation panel: CD3, CD4, CD8, CD25, CD127, CD45RA, Ki67, FoxP3, HLA-DR, CTLA-4, PD-1, CD27; 2) Dendritic cell panel:

CD1c/BDCA-1, CD202/BDCA-2, CD141/BDCA-3, M-DC8 (Sulph-LacNac), CD14, CD11c, CD16, CD19, CD40, CD80, PD-L1; 3) Myeloid-derived suppressor cell panel: CD11b, CD14, CD33, CD3/19/56 (Lin), HLA-DR, CD15, CD16, PD-L1. By performing these analyses at the indicated time points, we will gain unique insight in the kinetics of T cell activation following SBRT and PD-1 blockade and pre-, on- and post-treatment immune effector/suppressor subset profiles that may show differences between the two treatment arms, as we previously showed in a trial of combined ipilimumab and Prostate GVAX immunotherapy (76-78).

7.1.2.11 Ultrasound endoscopy guided cytological lymph node aspiration for immunological cell composition (EBUS FACS)

Patients will undergo an EBUS-FNA of the ipsilateral and contralateral hilar and mediastinal lymph nodes within 2 weeks before and between week 2 and 3 after SBRT (see section 5.4).

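### Section 8.2.2 assigns a paired t-test to four time levels when five blood samples are drawn, leaves the post-surgery sample undefined, and names no contrast for hypothesis 2

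*Combined protocol and SAP*

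**What the plan says.** Section 8.2.2 covers immunophenotyping in peripheral blood. Parameters are "compared within each patient (baseline vs on-treatment vs post-induction vs post-surgery"), and also between the two arms, "with the use of the paired t-test and the independent samples t-test, respectively". That is four time levels for the within-patient comparison.

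Section 7.1.2.10 schedules the blood draws "at t = 0, 21 days (immediately prior to 2nd therapeutic dose), just before surgery, one week after surgery and after 6 months", which is five time points, and adds: "Heparinized blood (40 ml) will be taken at each of these time points". The flow chart in section 6.1 does not separate the last two draws. Its single follow-up column runs "From surgery to 6 months thereafter".

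Hypothesis 2 in section 3.1 expects immune changes in tumor-draining nodes, tumor and blood, and a larger response in the combination arm than in the SBRT-alone arm. On size, section 5.2 states: "The sample size of 10 patients in each arm is based on two previous analyses that we performed", and "A formal power analysis to calculate a sample size is not feasible due to the explorative nature of this trial". Section 8 gives no significance level, no list of contrasts for blood and no approach to multiplicity.

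**The concern.** A paired t-test compares two measurements. Section 8.2.2 names it for four levels, so the analyst must choose which pairs to test, and the plan does not make that choice. Sections 8.2.1 and 8.2.3 do: there the within-patient comparison is post-induction against baseline.

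The sampling schedule and the analysis levels also differ in number. Baseline, on-treatment and post-induction map naturally to t=0, day 21 and the pre-surgery draw. Post-surgery could be either of two draws taken months apart.

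Blood is one of three compartments under primary objective 2. Hypothesis 2 is a statement about a difference between arms in the size of the response. Section 8.2.2 lists within-patient tests and between-arm tests, but does not say that change is compared between arms, or at which draw. Without that, the contrast, and which post-surgery sample stands for its level, can be picked after the data are seen.

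**Working it through.** **Sample count.** Section 7.1.2.10 lists 5 draws of 40 mL: 5 × 40 = 200 mL, which matches the PBMC row of Table 8. The table total also reproduces: 16 + 16 + 200 + 14 = 246 mL, as in section 10.3.8. So there are five samples against four analysis levels. The sample size of 20 cannot be reproduced, because no alpha, power, effect size or SD is given.

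**Number of within-patient tests per parameter.** All pairs of k levels number k(k−1)/2; comparisons with baseline number k−1.
- Four levels: 4×3/2 = 6 pairs, or 3 against baseline.
- Five draws: 5×4/2 = 10 pairs, or 4 against baseline.

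If the paired tests are run separately in each arm, which the plan does not say, 6 to 10 becomes 12 to 20.

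**Chance of at least one p<0.05 when nothing changes.** Two-sided 0.05 per test is an assumption, because section 8 states no level. If the tests were independent, the chance would be 1 − 0.95^m:
- m=6: 26.5%; m=10: 40.1%
- m=3: 14.3%; m=4: 18.5%

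Paired tests on the same patients are correlated, so these figures are too high. Simulating 40,000 trials with normal data and equal within-patient correlation 0.5 gives:

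| Tests made | n=10 (one arm) | n=20 (both arms together) |
|---|---|---|
| 6 (all pairs, four levels) | 21.5% | 20.9% |
| 10 (all pairs, five draws) | 30.6% | 29.8% |
| 3 (baseline only, four levels) | 13.2% | 12.4% |
| 4 (baseline only, five draws) | 16.0% | 15.7% |

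Under equal correlation the patient effect cancels from every difference, so the value of the correlation hardly matters: separate runs of 20,000 at 0.3 and 0.6 gave 21.9% and 21.6% for six tests, and 31.4% and 30.7% for ten. A serial (AR(1)) correlation of 0.6 gave 20.5% and 28.9%.

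If the arms are also compared at every time point, the corresponding figures at correlations of 0.3 and 0.6 are 17.4% and 14.8% (four times) and 21.1% and 16.9% (five). That reading is inferred: section 8.4 specifies testing per time point for CT data, section 8.2.2 does not. It also counts the t=0 comparison, which is not a treatment effect.

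**Which arm contrast to name.** Let r be the correlation between t=0 and pre-surgery values, with equal variances. Relative to comparing arms on the pre-surgery value alone (variance 1), the variance is:
- unadjusted change from t=0: 2(1 − r), which is 1.4 at r=0.3 and 0.8 at r=0.6
- adjusted for the t=0 value: 1 − r², which is 0.91 at r=0.3 and 0.64 at r=0.6

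A raw change score can therefore be worse than ignoring baseline. Adjustment is better than both at either correlation.

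**The case against.** The strongest reply is that this is a 20-patient mechanism study, called exploratory throughout, with no formal power analysis. The only pass/fail rule in section 8 concerns pneumonitis, and no decision turns on a blood p-value. That stands, and it limits how much weight family-wise error deserves. It does not settle which sample is the post-surgery value or which pairs are tested.

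A second reply is that the arms are randomised, so an independent samples t-test at a post-baseline draw already bears on hypothesis 2. That is partly right, but section 8.2.2 names no draw for it and does not say whether values or changes are compared.

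A reader might infer three stronger things that the documents do not support:
- **That the 1-week and 6-month samples are pooled.** Nothing says so. A paired t-test needs one value per patient per level, so either draw could be the one used, or each could be tested in turn. Section 7.1.2.10 stresses kinetics, which points away from averaging. The defect is a missing mapping rule.
- **That the 1-week sample mainly reflects surgical trauma.** It may be plausible, but the protocol does not state it and the point does not need it.
- **That every parameter will get 6 to 10 uncorrected tests.** These counts hold only if all pairs are tested, and uncorrected means only that no correction is mentioned.

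Paired tests also lose a patient from each comparison with a missing draw. That is true in general, but no expected missingness is given, and section 5.11 replaces patients who do not complete all three treatments.

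**Conclusion.** The concern holds in a limited form. Section 8.2.2 names a two-measurement test for four levels, does not assign the two post-surgery draws to a level, and ties no stated contrast to hypothesis 2. The mismatch between five samples and four levels is plain from the text and needs no assumption.

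The size of the false-positive problem does rest on assumptions: two-sided 0.05 per test, n=10, normal data and no true change. It is about 22% per parameter for six tests and 31% for ten, falling to about 13 to 16% if only baseline comparisons are made. These figures are per parameter, before the three marker panels are counted. They are chances, not a prediction that false findings will occur. The matter should be settled before the blood data are analysed, mainly because a better method is cheap and answers the stated hypothesis directly.

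**What to change.** In section 8.2.2, analyse each blood parameter with one repeated-measures mixed model containing arm, time and arm-by-time, a random patient effect and small-sample degrees of freedom. Keep the five draws as separate time points. Use the t=0 value in one of two ways: keep it as a fifth outcome level with the arms constrained equal there, or enter it as a covariate with the four later draws as outcomes.

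Name one key contrast per parameter: the baseline-adjusted arm difference at the draw just before surgery. This corresponds to hypothesis 2 and does not depend on either post-surgery sample. Report all other contrasts as exploratory estimates with 95% intervals, with the 1-week and 6-month results shown separately. If the sponsor prefers to keep t-tests, the minimum is to map all five samples to levels and name the key within-patient pair and the key arm comparison.

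The cost is SAP wording and slightly more analysis work, with no new samples or visits. Fewer contrasts can be called significant. That is preferable to a Bonferroni split over all pairs: with n=10 and 80% power, the detectable standardised within-patient change rises from 1.00 at 0.05 to 1.37 at 0.05/6 and 1.48 at 0.05/10. Multiplicity across parameters remains, and the SAP should say that these analyses are exploratory for that reason.

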2.2 Trial Diagram

3.0 OBJECTIVES & HYPOTHESES

3.1 Primary Objectives & Hypotheses

Objective 1:

To assess the safety of combined SBRT and pembrolizumab treatment.

Objective 2:

To identify the immunological response to combined SBRT and pembrolizumab treatment in early stage NSCLC. Expression rates and activation states of immune effector subsets will be assessed in tumor core biopsy specimens, peripheral blood and tumor draining lymph nodes (TDLNs) by means of EBUS derived fine needle aspirates. Samples will be taken before and after SBRT +/- pembrolizumab treatment and at surgery.

Hypothesis 2:

We anticipate that SBRT and pembrolizumab treatment will alter the immune activation status as well as the cellular composition in TDLNs, tumor and blood reflected by local and/or systemic switches from a suppressive immune content to a more activated immune content. The magnitude of this response is higher in the combination SBRT and pembrolizumab group than in the SBRT monotherapy group.

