5.4.1 Quantitative changes in lung density

The aim of these measurements is to determine whether a relationship exists between SBRT dose and radiographic lung injury, as measured by CT density changes (70).

Contours of selected isodose levels (0.5 Gy, 3 Gy, 6 Gy, 12 Gy, 18 Gy, 24 Gy, 36 Gy, and 50 Gy) will be exported from the planning system along with the contours of the lung and internal target volume, and the average-intensity CT dataset. These isodose lines are chosen to provide a wide range of doses and large enough volumes between lines to allow for meaningful density measurements. This results in a total of eight evaluable dose-density regions in the ipsilateral lung. In the contralateral lung, only one dose-density region (receiving ≥ 3 Gy) will be analyzed, because it is uncommon for the contralateral lung to receive >5 Gy. The contralateral lung receiving <3 Gy will be considered unirradiated and as such used to correct for baseline differences between scanners. The regions receiving >50 Gy are not analyzed because these volumes are small and because small errors in registration can place a few millimeters of regressing or stable tumor within that volume, artificially increasing density measurements. After deformation of the follow-up scans, isodoses from the endinspiratory phase of the planning CT scan will then be overlaid on the deformed follow-up scan, and changes in Hounsfield unit (HU) density assessed.

The air-filled fraction (f_{air}) will be calculated from HU density using the formula $f_{\text{air}} = \frac{HU - NCT}{-1000 - NCT}$, where NCT is the CT number in HU (71). f_{air} represents the percentage of lung tissue that contains air, and it decreases with increasing CT density.

5.5 Ultrasound endoscopy guided cytological lymph node aspiration for immunological cell composition (EBUS FACS)

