5.5.1 Bronchoscopy and EBUS procedure

EBUS-FNA of the ipsilateral and contralateral hilar and mediastinal lymph nodes will be performed within 2 weeks before and between weeks 2 and 3 after SBRT. Patient preparation and sedation will be performed according to regular institutional practice. Needle aspirations will be performed with a 22-gauge needle and 15 passages of the needle per lymph node. The ipsilateral hilar and mediastinal TDLNs will be sampled.

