7.1.4.1 Screening

7.1.4.1.1 Screening Period

Visit requirements are outlined in Section 6.0 - Trial Flow Chart. Specific procedure-related details are provided above in Section 7.1 - Trial Procedures.

Potential subjects will be evaluated to determine that they fulfill the entry requirements as set forth in Section 5.1. Written consent must be obtained prior to performing any protocol specific procedure. Results of a test performed prior to the subject signing consent as part of routine clinical management are acceptable in lieu of a screening test if performed within the specified time frame. Screening procedures are to be completed within 30 days prior to the first dose of trial treatment except for the following:

- Laboratory tests are to be performed within 10 days prior to the first dose of trial treatment.
- Tumor imaging must be performed within 14 days prior to the first dose of trial treatment.

Subjects may be rescreened after initially failing to meet the inclusion/exclusion criteria. Results from assessments performed during the initial screening period are acceptable in lieu of repeating a screening test if performed within the specified time frame and the results meet the inclusion/exclusion criteria.

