8.2.3 Immunophenotyping on lymph nodes using EBUS-FACS analysis

Absolute values of the individual immune cells will be calculated for TDLNs and NTDLNs.

The percentage difference between TDLNs, NTDLNs, peripheral blood and immune cells isolates from the resection specimen will be calculated and values will be quantified on a linear scale and compared within each patient (postinduction vs baseline) and between the treatment arms (SBRT vs SBRT + pembrolizumab) with the use of the paired t-test and the independent samples t-test, respectively.

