8.4 Analysis of CT data

The pre- and post SBRT +/- pembrolizumab CT scans will be assessed for HU density and f_{air} values as outlined in section 5.4.1. Baseline and post induction treatment values within patients will be assessed by the paired t-test. Comparison of the baseline and posttreatment values between the radiotherapy and radiotherapy + pembrolizumab arms will be assessed per time-point by the independent samples t-test.

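### Blood, EBUS-FACS and CT density are compared between arms without the scheduled baseline, at a modest cost in precision and, for blood and EBUS, with the compared quantity left unstated

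*Combined protocol and SAP*

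**What the plan says.** Hypothesis 2, under the primary objectives in section 3.1, is a statement about response in one arm against the other: "The magnitude of this response is higher in the combination SBRT and pembrolizumab group than in the SBRT monotherapy group".

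The between-arm analyses are:

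- **Blood (8.2.2).** Parameters are compared within each patient and "between the treatment arms (SBRT vs SBRT + pembrolizumab) with the use of the paired t-test and the independent samples t-test, respectively". The paired test serves the within-patient comparison and the independent samples test the comparison of arms.
- **EBUS-FACS (8.2.3).** The same two tests are used. A percentage is defined, but it is taken between compartments, not from baseline: "The percentage difference between TDLNs, NTDLNs, peripheral blood and immune cells isolates from the resection specimen will be calculated".
- **CT density (8.4).** "Comparison of the baseline and posttreatment values between the radiotherapy and radiotherapy + pembrolizumab arms will be assessed per time-point", again by independent samples t-test.

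No change score or baseline covariate is named in any of them. Each measurement nevertheless has a pre-treatment value in both arms. Blood immunophenotyping "will be performed at t = 0, 21 days (immediately prior to 2nd therapeutic dose), just before surgery" and twice after it (7.1.2.10). EBUS aspiration "will be performed within 2 weeks before and between weeks 2 and 3 after SBRT" (5.5.1). For CT, section 7.1.4.1.1 says "Tumor imaging must be performed within 14 days prior to the first dose of trial treatment", and section 5.4 repeats the chest CT shortly before resection. Section 5.4.1 defines where density is read: "This results in a total of eight evaluable dose-density regions in the ipsilateral lung", plus one region in the other lung.

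**The concern.** A test of follow-up values alone ignores each patient's own starting level. With 10 per arm, chance differences at baseline are not small: their standard error is sqrt(2/10) = 0.45 SD. The within-arm paired tests do not fill the gap, because they do not compare the arms.

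For blood and EBUS the plan also does not say whether values or changes enter the between-arm test. Raw values are the more natural reading of the text, but Hypothesis 2 speaks of the magnitude of a response. In an open-label trial that choice could be made after the data are seen. Section 8.4 is explicit about raw values per time-point, and so includes a between-arm test at baseline. After randomisation that test is uninformative.

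Adjustment has a condition of its own here. The 89Zr-pembrolizumab tracer goes to one arm before treatment, so a blood or EBUS baseline taken after it could already differ between arms for a reason other than chance.

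**Working it through.** **Inputs.** Section 5.2 gives 10 patients per arm and no power calculation, so there is no planned figure to reproduce. Two-sided 5%, a 1-SD difference and correlations r = 0.3, 0.5, 0.7 between baseline and follow-up are assumptions.

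**Step 1: power without a tracer effect.** The noncentrality is (1/s) / sqrt(2/10) = 2.236/s, where s is the SD of the analysed quantity relative to the raw value:

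- raw: s = 1, df = 18
- change: s = sqrt(2(1 - r)) = 1.183 / 1.000 / 0.775, df = 18
- ANCOVA: s = sqrt((1 - r²)(1 + 1/16)) = 0.983 / 0.893 / 0.736, df = 17

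| | r = 0.3 | r = 0.5 | r = 0.7 |
|---|---|---|---|
| Power, raw | 56% | 56% | 56% |
| Power, change | 43% | 56% | 78% |
| Power, ANCOVA | 57% | 66% | 82% |
| Detectable difference at 80% power, raw (SD) | 1.32 | 1.32 | 1.32 |
| Same, change | 1.57 | 1.32 | 1.03 |
| Same, ANCOVA | 1.31 | 1.19 | 0.98 |

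Simulation from a bivariate normal model agrees, and all three methods hold about 5% type I error. The raw-or-change choice moves power by -13, 0 or +22 points. ANCOVA against raw gives +1, +10 or +25 points (unrounded simulated values). At r = 0 it gives 53.8% against 56.4%, a loss of 2 to 3 points, and it breaks even near r = 0.25.

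**Step 2: missing baselines.** Section 5.5.2 makes the EBUS subsets depend on cell yield. Suppose 2 of 10 per arm have a follow-up value but no usable baseline. If they are dropped, ANCOVA on 8 per arm has 46 / 54 / 70% power, while the planned raw test on all 10 has 56%: a change of -10 / -2 / +14 points. Adjustment that drops patients can therefore lose power.

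**Step 3: tracer timing.** Section 4.2.3 and the flow chart (6.1) restrict the tracer to the combination arm, before treatment. Section 5.3.2.5 puts the last scan at 144 h, and 144/24 = 6 days, so injection falls on day -6 or earlier. The flow chart places the tracer PET, baseline EBUS and first immunophenotyping sample in one column, day -14 to 0. At least the last 6 of those 14 days follow the injection. Section 7.1.2.10 does not define t = 0. If it means the first treatment day, the combination-arm blood baseline is drawn 6 or more days after the tracer.

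**Step 4: what a shifted baseline would do.** Let the tracer move the combination-arm baseline by d SD and leave follow-up unchanged. The bias is 0 for raw, -d for change and -(r × d) for ANCOVA. Type I error at r = 0.3 / 0.5 / 0.7:

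| Assumed d | Raw | ANCOVA | Change |
|---|---|---|---|
| 0.1 | below 6% | below 6% | below 6% |
| 0.25 | 5% | 5 / 6 / 8% | 7 / 8 / 10.5% |
| 0.5 | 5% | 6 / 9 / 16% | 15 / 18 / 28% |

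With a true 1-SD effect and d = 0.5 in the same direction, ANCOVA power is 43 / 41 / 44%, below the raw test's 56%.

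**The case against.** The strongest reply is that nothing planned here is invalid. The t-test on follow-up values is unbiased under randomisation, section 5.2 disclaims formal power, and the documents give no correlation; at 0.3 the gain from ANCOVA is about one point. All of that stands and limits the size of the point.

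A reader might infer from the timing that the blood and EBUS baselines are contaminated, or that no baseline-adjusted analysis of them could be valid. The documents do not support this. Nothing in them shows that 2 mg, which is 2/200 = 1% of one treatment dose, shifts any readout. PD-1 is in the blood panel, so an effect is plausible, but d is an assumption and may be negligible. For EBUS, section 10.3.9 describes the baseline procedure as regular staging, and N0 disease is an entry criterion, so it probably precedes the tracer. The flow chart merely permits the other order. Section 5.3.2.5 also describes the scans as applying to every patient, against section 4.2.3 and the flow chart. If every patient did receive the tracer, the asymmetry would disappear.

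A reader might equally take CT adjustment to be free of conditions. It is so only if the baseline scan is of one type for all patients. Section 5.4.1 works from planning-CT isodoses, and section 5.6.1.1 does not require a 4-D planning scan with MR-guided SBRT.

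The missing-baseline objection in Step 2 succeeds against any adjustment that discards patients, and the fix has to meet it.

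**Conclusion.** The point holds as a modest matter of precision and pre-specification in an exploratory trial. Sections 8.2.2, 8.2.3 and 8.4 leave out a baseline that the trial already collects, and for blood and EBUS the compared quantity is not stated. It would go too far to call the planned comparisons biased: they hold 5% type I error.

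The gain from ANCOVA is 1 to 25 points of power over assumed correlations of 0.3 to 0.7 for an assumed 1-SD effect, with a loss of 2 to 3 points at zero correlation. An unadjusted change score is not a safe substitute. It is less precise than the raw test below a correlation of 0.5, and it takes the full bias if the baseline shifts. The tracer is a reason to fix the order of sampling, not evidence of an effect. All figures assume normal data.

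**What to change.** 1. **Section 8.4.** Replace the between-arm t-tests with ANCOVA of the post-induction value on arm and the patient's own pre-treatment value, separately for each dose-density region, with a 95% CI. Name one baseline scan type for all patients. Drop the between-arm test at baseline.
2. **Sections 8.2.2 and 8.2.3.** State that follow-up values are compared, adjusted for baseline by ANCOVA at each post-baseline time-point, and that unadjusted change scores are not used between arms. Define t = 0 and the baseline EBUS as taken before tracer injection; for EBUS this can be the staging procedure. Check sampling dates before results are seen. If a compartment has no pre-tracer baseline, keep the unadjusted follow-up comparison for it.
3. **Missing baselines.** Keep every patient with a follow-up value. Fill a missing baseline with the mean pooled over both arms, or keep the unadjusted test for subsets where many baselines are missing.
4. **Left as planned.** Section 8.2.1 and the contrasts in 8.2.3 that use resection isolates, which have no baseline, stay unadjusted. The paired tests remain as within-arm description.
5. **Reconcile** section 5.3.2.5 with section 4.2.3 and the flow chart on who receives the tracer.

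The cost is SAP wording, a stated sampling time and one degree of freedom per comparison. The t = 0 blood draw may have to move earlier, possibly to another visit in the SBRT-only arm. If a treatment-day sample is also wanted, that is one extra 40 mL draw, taking the planned total from 246 to 286 mL.
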